additional 5 active and 5 placebo subjects will be dosed (no more than 2 subjects per day with dosing separated by at least 1 hour). Once data up to 28 days post dose has been collected for all subjects within the cohort, the DEC will review the safety data along with the available PD data, before dosing a cohort of healthy volunteers with pre-existing ADA, at the same dose, without DTH.

A study schematic giving an overview of the visits is in Section 3.1.

Screening - Subjects will attend screening up to 35 days before the first PPD challenge.

Day 1 to Day 3 - Subjects will attend the unit on Day 1 and will receive ID injections of PPD as per Section 5.10.1 and Section 6.5.1. A skin biopsy will be taken from one of the DTH sites as detailed in Section 6.8.1.

Day 28 to Day 32 - After a period of at least 28 days (\pm 3 days) from the first challenge, subjects will return to the unit and will remain resident in the unit from Day 28 (\pm 3 days) until at least 72 hours after dosing. Subjects will receive ID injections of PPD as per Section 5.10.1 and Section 6.5.1. A skin biopsy will be taken from one of the DTH sites as detailed in Section 6.8.1. Provided there are no safety issues and there are no clinically significant haematology results on Day 32 (72 hours post dose) the subject will be discharged from the unit.

Days 36 and beyond dependent on dose group - Subjects will attend the unit as an out-patient.

Follow-up - Subjects will return for a follow-up as specified in Table 1

As the follow-up visit is at approximately 6 months (190 days post-dose, as per Table 1), subjects in the 0.15mg/kg cohort do not require an additional post-dose surveillance visit at 6 months and will only attend a surveillance visit at 12 months.

PART B

Psoriasis patients

At the beginning of Cohort 7, sentinel dosing in subjects without pre-existing ADA will occur such that one subject will receive active and one subject will receive placebo. After review of the two sentinel subjects' safety data (Cohort 7) at 48 hours post-dose, an additional 5 active (3 without and 2 with pre-existing ADA) and 2 placebo subjects (1 with and 1 without pre-existing ADA) will be dosed (no more than 2 subjects per day with dosing separated by at least 1 hour).

All subsequent cohorts do not require stratification for pre-existing ADAs.

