Protocol Activity		st lenge					In C	linic Per	iod								Out P	atient	Visits	5			
			Day 28			Day	29 (Day ′	1)		Day 30 (Day 2 post- dose)		Day 32 (Day 4 post- dose)											
	Day 1	Day 3	Day 28	Pre- dose	0 hour	2 hour post- infusion start	4 hour post- infusion start	post-	post-	24 hour post- infusion start	48 hours post- infusion start	start	(Day 8 post-	11 post-	15 post-		22 post-	25 post-	29 post-		Day 85 (Day 57 post- dose)		121 post-
Window			±3d										±1d	±1d	±1d	±1d	±1d	±1d	±1d	±2d	±2d	±2d	±3d
Efficacy Assessn	nents																						
Visual Arm Inspection	Xď									Xe													
ID PPD Challenge	Xf									Xf													
Bleb/ILH Assessment	Xe									Xe													
Ball Point Pen Technique		х										х	х		Х		Х						
Skin Biopsy		Xg										Xg											

CONFIDENTIAL

Protocol Activity	1 Chal	st lenge					In C	linic Per	iod								Out P	atient	Visits	;			
			Day 28			Day	29 (Day 1	1)		Day 30 (Day 2 post- dose)	Day 31 (Day 3 post- dose)	Day 32 (Day 4 post- dose)											
	Day 1	Day 3	Day 28	Pre- dose	0 hour	2 hour post- infusion start	4 hour post- infusion start	post-	post-	24 hour post- infusion start	48 hours post- infusion start	72 hour post- infusion start	(Day 8 post-		15 post-	18 post-		25 post-	29 post-		Day 85 (Day 57 post- dose)		
Window			±3d										±1d	±1d	±1d	±1d	±1d	±1d	±1d	±2d	±2d	±2d	±3d
Laboratory Asses		nts		-						-						-						-	
Haematology			Х					Х	Х			Х	Х	Х	Х	Х	Х	Х	Х	Х	Х	Х	Х
Chemistry	X ^h		Х					Xi	Xi			Х	Х		Х		Х		Х	Х	Х	Х	Х
Urinalysis	Xh		Х					Х	Х			Х	Х		Х		Х		Х	Х	Х	Х	Х
CMV and EBV serology sample			Х																				
Viral load sample (CMV, EBV, HSV, VZV) ^j			х																				
Immunogenicity Sample				Х									Х						Х			Х	
PK Sample ^k					◀																>	-	
Immune Cell Phenotyping ⁱ				Х				Х		Х		Х	Х		Х				Х		Х	Х	х
CD16 and LAG-3 Receptor occupancy				х				Х		х		х	х		Х				Х		Х	х	x
Cytokine Sample				Х				Х	Х	Х	Х												
G-CSF Sample				Х				Х		Х		Х	Х		Х				Х	Х	Х	Х	Х

CONFIDENTIAL

Protocol Activity	1 Chal	st lenge					In C	linic Per	iod								Out P	atient	Visits	;			
			Day 28			Day	29 (Day ′	1)		Day 30 (Day 2 post- dose)	Day 31 (Day 3 post- dose)	Day 32 (Day 4 post- dose)											
	Day 1	Day 3	Day 28	Pre- dose	0 hour	2 hour post- infusion start	4 hour post- infusion start	post-	post-	24 hour post- infusion start	48 hours post- infusion start	start	(Day 8 post-	11 post-	15 post-	18 post-	22 post-	25 post-		43 post-		Day 113 (Day 85 post- dose)	

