9. DATA ANALYSIS AND STATISTICAL CONSIDERATIONS

9.1. Hypotheses and Treatment Comparisons

The primary objective is to determine the safety and tolerability of single IV Doses of GSK2831781 in healthy volunteers and in patients with mild to moderate psoriasis.

There are no formal hypotheses planned.

An assessment of dose proportionality of AUC and Cmax, following single dosing, will be conducted separately for healthy volunteers and patients with psoriasis.

Where appropriate, an estimation approach will be used to address the study objectives where point estimates and corresponding confidence intervals will be constructed to provide a plausible range of values for the comparison of interest.

Exploratory comparisons will be conducted to investigate the effect of ADA status at baseline on the pharmacokinetics of GSK2831781.

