8. EFFICACY ANALYSES

8.1. DTH Induration (only for HV)

8.1.1. Endpoint / Variables

- The induration diameter (mm) by challenge site is defined as the average of the 2 skin response test values (vertical and horizontal) at each challenge site.
 A challenge site is defined by skin response (SR) directionality (upper/lower) and SR laterality (left/right). There are 4 categories:
 - Left upper
 - Right upper
 - Left lower
 - Right lower
- 2. The overall induration diameter (mm) is defined as the average of the non-missing induration diameters over the challenge sites.
- 3. The duration of induration is the time (in days) to achieve an overall induration less than 6mm from baseline (see Section 5.2 for baseline definition). It will be calculated as: Date of 1st overall induration < 6mm Date of baseline induration assessment + 1. For these subjects who do not achieve an overall induration less than 6mm from the time of the PPD re-challenge post dose, the duration of induration is calculated as time from the PPD re-challenge post dose up to the last available induration measurement +1.

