8.1.4.1. Statistical Methodology Specification

Endpoint

Change from baseline in induration diameter (mm) (Overall induration diameter only)

Model Specification

- Mixed models repeated measures (MMRM) model.
- Terms fitted in the MMRM model will include:
 - Fixed categorical covariates: Treatment, day (visit), treatment * day (visit) interaction
 - Fixed continuous covariates: Baseline (see Section 5.2 for baseline definition)
 - Repeated: Day (visit)
- An unstructured covariance will be used to account for the within-subject correlation. by specifying 'type=UN' on the REPEATED line.
- The Kenward and Roger method for approximating the denominator degrees of freedom and correcting for bias in the estimated variance-covariance of the fixed effects will be used.
- LSmeans of the CFB will be calculated using the observed margins (OM argument added in the LSmeans function)

Model Checking & Diagnostics

 In the event that this model fails to converge, alternative correlation structures may be considered.

Model Results Presentation

Table/Figure of the LS means and 95% CI (by treatment and visit)

Endpoint / Variables

Duration of induration of at least 6mm (days)

Model Specification

Hasard ratios will be estimated using the Pike estimator.

Model Results Presentation

- Summary table of the hazard ratios
- No plot

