14.9.14. Non-ICH Listings

Non-ICH: Listings					
No.	Population	IDSL / Example Shell	Title	Programming Notes	Deliverable
32.	PK	PK07	Listing of plasma GSK2831781 pharmacokinetic concentration-time data for healthy volunteers		IA2 W2
33.	PK	PK07	Listing of plasma GSK2831781 pharmacokinetic concentration-time data for psoriasis patients		IA2 W2
34.	PK	PK13	Listing of derived plasma GSK2831781 pharmacokinetic parameters for healthy volunteers		IA2 W2
35.	PK	PK13	Listing of derived plasma GSK2831781 pharmacokinetic parameters for psoriasis patients		IA2 W2
36.	Safety	IMM2	Listing of immunogenicity results for healthy volunteers	NAB assay results included for SAC	IA2 W2
37.	Safety	IMM2	Listing of immunogenicity results for psoriasis patients	same as for HV	IA2 W2
38.	Safety		Listing of induration diameter for healthy volunteers (DTH subjects)		IA1
39.	Safety		Listing of duration of induration for healthy volunteers (DTH subjects)		IA1
40.	safety		Raw sas output statistical analysis results of change from baseline in induration diameter for healthy volunteers (DTH subjects)		IA1
41.	safety		Raw sas output statistical analysis results of duration of induration for healthy volunteers (DTH subjects)		IA1
42.	Safety	LS1	Listing of PASI-related endpoints for psoriasis patientss		SAC
43.	Safety		Listing of PASI components for psoriasis patients		SAC

Non-IC	Non-ICH: Listings					
No.	Population	IDSL / Example Shell	Title	Programming Notes	Deliverable	
44.	Safety		Listing of BSA scores for psoriasis patients		SAC	
45.	Safety		Raw sas output of statistical analysis results for change from baseline in PASI scores for psoriasis patients		IA2 EFF IA2	
46.	Safety		Raw sas output of statistical analysis results for change from baseline in PLSS score for psoriasis patients		IA2 EFF IA2	
47.	Safety		Listing of PLSS-related endpoints for psoriasis patients		SAC	
48.	Safety		Listing of PGA-related endpoints for psoriasis patients		SAC	
49.	Safety		Listing of cytokines for healthy volunteers		IA1	
50.	Safety		Listing of cytokines for psoriasis patients		SAC	
51.	Safety		Listing of flow cytometry for healthy volunteers	All the parameters, not only the 6 key ones	IA1	
52.	Safety		Listing of flow cytometry for psoriasis patients	All the parameters, not only the 6 key ones	SAC	
53.	Safety		Listing of LAG3+ and CD3+ in skin for healthy volunteers (DTH subjects)		IA1	
54.	Safety		Listing of cells in lesional biopsies measured by IHC for psoriasis patients		SAC	

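### The Pike estimator named for the DTH duration hazard ratio is strongly biased towards 1 when the effect is large, with 6 v 6 subjects and four readings

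*SAP*

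**What the plan says.** Duration of induration in the re-challenge is a secondary endpoint (Protocol section 2; SAP section 2.2).

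- **Definition.** SAP section 8.1.1: "The duration of induration is the time (in days) to achieve an overall induration less than 6mm from baseline". It is written with calendar dates. Subjects who never fall below 6 mm are instead timed from the re-challenge to their last measurement.
- **Method.** SAP section 8.1.4.1: "Hasard ratios will be estimated using the Pike estimator". The output is "Summary table of the hazard ratios". No formula, tie rule, variance, confidence interval or test is given.
- **Subjects.** After a sentinel pair, an "additional 5 active and 5 placebo subjects will be dosed" (Protocol section 3.2), which makes 6 v 6.
- **Readings.** In Protocol Table 8 the "Ball Point Pen Technique" row is marked after re-challenge only at post-dose Days 4, 8, 15 and 22.
- **Time scale.** SAP section 14.4.2 uses planned time unless stated otherwise.
- **Inference.** Protocol section 9.1 states that, where appropriate, "point estimates and corresponding confidence intervals will be constructed to provide a plausible range of values for the comparison of interest". No formal hypotheses are tested.
- **Where it appears.** Table 2.3 (SAP section 14.9.5) and Listing 41 (section 14.9.14) are both Interim 1 deliverables. A note on Table 2.3 removes the hazard ratio if that table is needed for the final reporting.

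**The concern.** The Pike estimator compares observed counts with log-rank expected counts computed as if the arms had equal hazards. That reference works near a hazard ratio of 1 with few ties. With six subjects per arm and four possible event times it fails when the drug works. At the visit where active subjects resolve together, half of those events are charged to a placebo arm that had none, and later placebo events fall wholly on placebo. The ratio is then pulled towards 1.

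Interim 1 exists to inform internal decisions and the planning of later studies. A reader there could take a ratio of 2 or 3 as a modest effect on duration when the data are compatible with a much larger one.

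**Working it through.** The plan gives no hazard ratio, event count or interval for this endpoint, so there is no figure of its own to reproduce.

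**Formula.** HR = (O_A/E_A)/(O_P/E_P), where E_A is the sum over event visits of d × n_A/n (d events, n at risk, n_A of them active), and likewise E_P.

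**All active resolve at one visit, all placebo at any later visit(s).**
- E_A = 6 × 6/12 = 3; E_P = 3 + 6 = 9.
- HR = (6/3)/(6/9) = 3.0.
- Log-rank variance = 6 × 0.5 × 0.5 × 6/11 = 0.818; chi-square = (6 − 3)²/0.818 = 11.0; p = 0.0009.
- Exact permutation p = 2/924 = 0.002.

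**Other completely separated outcomes** (every active subject resolves before any placebo subject).

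| Outcome | Patterns | Pike HR |
|---|---|---|
| All 12 resolve, tied by visit | 91 | 3.0 to 4.22 (exactly 3.0 in 36) |
| Some placebo unresolved at the last reading | 280 | 3.2 to 12.3 |
| No placebo subject resolves | 84 | infinite (O_P = 0) |
| All 12 resolve, no ties at all | – | 4.77 |

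**Intervals for the HR 3.0 case.** The SAP names none, so these are assumptions.
- SE = √(1/3 + 1/9) = 0.667, the usual choice: 0.81 to 11.1.
- SE = √(1/6 + 1/6) = 0.577: 0.97 to 9.30.
- Test-based: 1.57 to 5.74.

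**Simulation of the point estimate.** 6 v 6, four visits, times from re-challenge, non-resolvers censored at the last reading, 4000 trials per cell. The placebo probability of resolving at each visit is h; the active probability is 1 − (1 − h)^HR. The documents give no placebo profile, so four are assumed.

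| Placebo h by visit | Placebo unresolved | Median Pike, true HR 4 | True HR 10 | True HR 20 |
|---|---|---|---|---|
| 0.05/0.4/0.6/0.8 | 5% | 1.9 | 2.4 | 2.7 |
| 0.1/0.3/0.5/0.7 | 9% | 2.2 | 2.8 | 2.9 |
| 0.05/0.2/0.4/0.6 | 18% | 2.3 | 3.0 | 3.2 |
| 0.05/0.1/0.2/0.3 | 48% | 3.0 | 4.0 | 4.3 |

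The unresolved share is the product of (1 − h), for example 0.95 × 0.8 × 0.6 × 0.4 = 0.18. With no effect the median is 1.0, so the bias comes with the effect. On the same data the log-rank test rejects at 5% in 43 to 50%, 72 to 86% and 88 to 97% of trials at true HR 4, 10 and 20.

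**Replacement model.** A grouped-time complementary log-log model with Firth penalisation, run on the first and third profiles with 250 to 600 trials per cell, gives medians of about 4 at true HR 4, 6 to 8 at 10 and 8 to 13 at 20. It rejects in 5 to 7% under no effect.

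**The case against.** Several stronger readings are tempting, and the documents do not support them.

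- **That complete separation always gives 3.0.** It is the minimum. Unresolved placebo subjects raise the ratio and no placebo events make it infinite.
- **That the planned interval would include 1, or that planned power is lost.** SAP section 8.1.4.1 plans no interval or test here, and Protocol section 9.1 calls for intervals only where appropriate. On the HR 3.0 data the test-based interval excludes 1. Power is not a design property of a study without formal hypotheses. The attenuation of the point estimate needs none of this.
- **That exact ties are certain.** The duration formula uses dates, with a ±3 day window before the dosing period and ±1 day on the last three readings. With uniform jitter of that size, active at Day 4 and placebo at Day 15, the median ratio is 4.4 and the 1/E interval excludes 1 in about 81% of simulations. This loosens the ties but does not cure the bias: with no ties and everyone resolved, complete separation still stops at 4.77. Much of the jitter also comes from the gap between first challenge and dosing, which says nothing about how long the re-challenge reaction lasts.
- **That the final analysis or study conduct would be misled.** The note on Table 2.3 drops the ratio from final reporting, and Interim 1 has no planned implications for conduct.
- **That the effect would go unseen.** Durations by arm, per-subject listings, induration plots and the repeated-measures model for diameter are also planned. With 12 subjects, non-overlap would be visible there.

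What stands is that the one comparative statistic named for this endpoint misstates the size of a large effect.

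**Conclusion.** The point holds for the estimate, not for an interval or a test. With visit-level times and 6 v 6 subjects, the Pike ratio has a median of about 2 to 3 when the true ratio is 4 and mostly about 2.5 to 3.5 when it is 10 to 20. The slowest placebo profile tried reaches 4.0 to 4.3. In the clearest separated case it reports 3.0 beside a log-rank p of 0.0009.

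This rests on assumed placebo profiles, proportional hazards, times taken from re-challenge and censoring of non-resolvers at the last reading. The harm is limited to Interim 1, where other displays would also show the effect. Severity is minor to moderate.

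**What to change.** Wherever a hazard ratio for this endpoint is reported, replace the Pike sentence in SAP section 8.1.4.1 along these lines: the active v placebo hazard ratio for induration falling below 6 mm will come from a grouped-time proportional hazards model (complementary log-log link; visit and treatment) on the Day 4, 8, 15 and 22 readings, with Firth penalisation and a penalised profile-likelihood 95% interval. Show beside it the exact permutation log-rank p-value and the number of subjects below 6 mm by visit and arm.

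Amend section 8.1.1 to match: time every subject from re-challenge and censor non-resolvers at the last reading. At present an event at Day 32 measured from a Day 3 baseline lasts 32 − 3 + 1 = 30 days, while a non-resolver followed from Day 30 to Day 50 has 50 − 30 + 1 = 21 days. If treated as censored, that subject would leave the risk set before any event.

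Apply this to Table 2.3 and Listing 41 only, without reinstating a hazard ratio in the final reporting. If Interim 1 has already been run (the documents do not say), a re-run or a caution beside the reported ratio would serve.

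The cost is SAP wording and a short program on data already collected. The drawbacks are wide intervals, a slightly liberal penalised test (hence the exact p-value) and some remaining attenuation at very large ratios.

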8.2. Body Surface Area (only for PsO)

8.2.1. Endpoint / Variables

Total body surface area (BSA), in %, measures the area covered with psoriatic plaques.

In the FACE dataset, 4 regional BSA scores (%) are available ((head, upper extremities, trunk, and lower extremities). The total BSA score for each subject at each timepoint is calculated as the sum of the 4 regional BSA scores. If at least one of the 4 regional BSA scores is missing, the total will be set to missing as well.

8.2.2. Summary Measure

Absolute BSA scores (4 regional and total), change from baseline and percent change from baseline in BSA scores over time.

8.2.3. Population of Interest

The efficacy analyses will be based on the Safety population.

8.2.4. Statistical Analyses / Methods

Details of the planned displays are provided in Appendix 9 and will be based on GSK data standards and statistical principles.

Unless otherwise specified, endpoints / variables defined in the section above will be summarised using descriptive statistics, and listed.

8.3. PASI-related endpoints (only for PsO)

8.3.1. Endpoint / Variables

Psoriatic lesions will be assessed using the PASI (Psoriasis Assessment Severity Index), single score ranging from 0 (no disease) to 72 (maximal disease). A negative (%) change from baseline in PASI score indicates an improvement.

The PASI score for each subject at each timepoint is derived as follows.

Data available (PASI SI dataset):

- Areas of the body: head (1), upper extremities (2), trunk (3), lower extremities (4)
- For each of the 4 areas of the body, the intensity of 3 symptoms is assessed on a 0-4-point rating scale
 - Symptoms: erythema (redness of the skin), induration (thickness) and scaling of the psoriasis

CCI - This section contained Clinical Outcome Assessment data collection questionnaires or indices, which are protected by third party copyright laws and therefore have been excluded.

• For each of the 4 areas of the body, the percentage area affected by psoriasis is evaluated and expressed as nil (0), 1-9% (1), 10-29% (2), 30-49% (3), 50-69% (4), 70-89% (5) or 90-100% (6)

Derivation

1. Calculation for intensity: the three intensity scores are added up for each of the 4 areas of the body to give 4 subtotals A1, A2, A3, A4.

CCI - This section contained Clinical Outcome Assessment data collection questionnaires or indices, which are protected by third party copyright laws and therefore have been excluded.

2. Multiply each subtotal (A1, A2, A3, A4) by the body surface area (BSA) represented by that region to give 4 new subtotals (B1, B2, B3, B4).

Note: The BSA will not be calculated using the palm's method as categories above are collected. Fixed weights are used.

CCI - This section contained Clinical Outcome Assessment data collection questionnaires or indices, which are protected by third party copyright laws and therefore have been excluded.

3. Multiply each subtotal (B1, B2, B3, B4) by the area affected (PASIAREA) for that region to give 4 new subtotals (C1, C2, C3, C4):

CCI - This section contained Clinical Outcome Assessment data collection questionnaires or indices, which are protected by third party copyright laws and therefore have been excluded.

- 4. Calculate the total PASI score = C1 + C2 + C3 + C4
- 5. If any variable is missing, set PASI score to missing

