4.2.1. Inclusion Criteria

A subject will be eligible for inclusion in this study only if all of the following criteria apply:

- 1. Part A males aged between 18 and 65 years of age and Part B males and females aged between 18 and 75 years of age inclusive at the time of signing the informed consent.
- Part A: A body weight ≤120 kg and BMI within the range 19 32 kg/m2 (inclusive). For healthy volunteer subjects participating in Germany the BMI must be within the range of 19 – 30 kg/m2 (inclusive). Part B: BMI within range 19-35 kg/m² (inclusive).
- 3. **Part A only:** Healthy as determined by a responsible and experienced physician, based on a medical evaluation including medical history, physical examination, laboratory tests and 12-lead ECGs. A subject with a clinical abnormality or laboratory parameter(s) which is/are not specifically listed in the inclusion or exclusion criteria, outside the reference range for the population being studied may be included only if the Investigator in consultation with the GSK Medical Monitor, if required, agree and document that the finding is unlikely to introduce additional risk factors and will not interfere with the study procedures.
- 4. **Part A DTH cohort only:** Subjects with a history of BCG vaccination as evidence by either:
 - A BCG scar and verbal confirmation of BCG vaccination
 - Or documented medical history of a BCG vaccination with or without a BCG scar
- 5. **Part B only:** Subject has psoriasis covering BSA ≥3% as assessed at Screening and Day -1.
- 6. **Part B only:** Subject has had a confirmed diagnosis of chronic plaque-type psoriasis (without recent documented flare within 30 days prior to screening) for at least 6 months.
- Part B only: Subject has at least 2 stable plaques assessed at Screening and Day -1. One of a suitable size and in a site suitable for repeat biopsy, and one for index lesion PLSS scoring. Both must have a PLSS lesional score of ≥2 for the induration component (moderate or above), ≥1 for erythema and scaling with a total score of ≥5. The biopsy lesion must not be on the face, groin or scalp and must be protected from the sun.
- 8. Part A only: Subjects with a history of vaccination for Tetanus, diphtheria, measles, pertussis, mumps and rubella.

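### The PASI missing-data rule discards a fully determined score when the only blank item is an intensity in a region with no psoriasis

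*SAP*

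**What the plan says.** SAP 8.3.1 builds PASI from 16 items per visit: three intensity items and one area item in each of four body regions.

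- Intensity: "For each of the 4 areas of the body, the intensity of 3 symptoms is assessed on a 0-4-point rating scale". Then "the three intensity scores are added up for each of the 4 areas of the body to give 4 subtotals A1, A2, A3, A4".
- Region weight: each subtotal is multiplied by a regional weight. "Fixed weights are used"; their values are redacted.
- Area: "Multiply each subtotal (B1, B2, B3, B4) by the area affected (PASIAREA) for that region". The area score runs from 0 (nil) to 6.
- Total: the four regional products are added. The stated range is 0 to 72.
- Missing data: "If any variable is missing, set PASI score to missing".

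The consequences follow elsewhere in the SAP. Section 8.3.2 sets the responder status to missing when PASI is missing. Section 8.3.4.1 fits a repeated-measures model to change from baseline. Section 13 takes each patient's lowest non-missing post-baseline value up to Day 85. Section 5.2 names Day -1 as the PASI baseline and performs no derivation when the baseline is missing. Protocol Table 6 schedules no PASI at screening.

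On who can enter, Protocol 4.2.1 requires only this: "Subject has psoriasis covering BSA ≥3% as assessed at Screening and Day -1".

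**The concern.** PASI is a sum of products, so an item multiplied by 0 cannot affect the total. The missing-data rule treats all 16 items alike and so can discard a score that is exactly known. A region with no psoriasis is also where an assessor might leave the erythema, induration and scaling fields empty. Appendix 5 (SAP 14.5.1) defines missing data as blank fields. It says that answers such as not applicable are not missing, but gives them no numeric value that could enter the PASI sum.

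With an entry threshold of 3% body surface area, regions can be clear from the start, and others may clear during the study. At stake are single visits in a very small trial or, if the blank is at Day -1, all of a patient's PASI results relative to baseline. PASI and PLSS are also the endpoints of the first stage of the second interim analysis, and SAP 14.9.5 lists the Bayesian output under go/no-go decisions.

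**Working it through.** **Inputs.** From SAP 8.3.1: three intensity items of 0–4 per region, so the subtotal A runs from 0 to 12; area score 0–6; fixed weights w (values redacted). From Protocol 3.1.2, Table 1: 6 active and 3 placebo patients per psoriasis cohort, so 9 placebo patients in all.

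**1. Reproduce the stated range.** PASI = Σ (A × w × area) over four regions. The maximum is 12 × 6 × Σw = 72 × Σw. The stated maximum of 72 therefore requires Σw = 72 / (12 × 6) = 1. The minimum is 0. The range of 0 to 72 reproduces.

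**2. A region with area score 0.** Its contribution is A × w × 0 = 0 for every A from 0 to 12 and any weight. All 125 combinations of the three intensity items (5 × 5 × 5) gave 0. In 1,000 random profiles with one nil-area region, the total did not move as that region's A ran over its 13 possible values (spread 0). The redacted weights do not matter.

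**3. Apply the rule as written.** Suppose region 1 has area score 0 and one blank intensity item, and the other regions are complete. The formula gives PASI = C2 + C3 + C4 exactly. The last step gives missing. In the extreme case all four area scores are 0: PASI is 0, yet one blank intensity makes it missing.

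**4. What is lost.**

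| Where the blank falls | What is lost |
|---|---|
| One post-baseline visit | That visit's PASI 50/75 status, that visit's record in the repeated-measures model, and that visit as a candidate for the Bayesian lowest score. The patient's other visits stay. |
| Day -1 | The patient's change from baseline, PASI 50/75 and Bayesian PASI result at all visits, unless an unscheduled pre-dose PASI exists. |

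**5. Scale, with assumed responder counts.** One patient is 1/6 = 16.7% of a dose group and 1/9 = 11.1% of placebo. Exact 95% intervals:

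| Change | Before | After |
|---|---|---|
| One responder lost, dose group | 2/6 = 33.3% (4.3–77.7) | 1/5 = 20.0% (0.5–71.6) |
| One non-responder lost, dose group | 2/6 = 33.3% (4.3–77.7) | 2/5 = 40.0% (5.3–85.3) |
| One responder lost, placebo | 3/9 = 33.3% (7.5–70.1) | 2/8 = 25.0% (3.2–65.1) |

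The counts are invented to show the scale. The first two rows show that the estimate can move either way. The documents give no count of blanks, so no expected effect can be computed.

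**The case against.** The strongest reply is that the blank should not occur. Protocol 6.4.2 has every region assessed for all three symptoms, and SAP 8.3.1 repeats this on a 0–4 scale. SAP 8.4.1 defines 0 on the plaque score as no symptoms, and Protocol 6.4.4 says that the plaque score uses the same scale as PASI. Read together, 0 is the expected entry for a clear region. Parts of the PASI text are redacted, and the protocol leaves further scoring detail to a procedures manual that is not available, so an explicit instruction may exist. Data cleaning and queries (Protocol 8, SAP 3.2) come before the final analysis and could resolve any blank. All of this stands. It makes the problem less likely, but it does not change what the last step does with a blank that remains. The PASI and PLSS interim evaluation at Day 43 (SAP 3.1) also comes before the final cleaning.

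A second reply is that requiring complete items is conservative and matches the body surface area rule in SAP 8.2.1. The parallel fails: regional surface areas add, so a missing one is truly unknown, whereas here the missing item is multiplied by a known 0. A small part of the reply stands: if an area score were wrongly entered as 0, the revised rule would accept it without the prompt that missing intensities give.

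A reader might also infer that the rule selectively removes responders. The documents do not support that. Regions can be clear at baseline, in patients on placebo and in non-responders, so blanks could fall on any of them. Post-baseline losses might fall more on improved visits, but this is not shown. Nor does one lost post-baseline visit drop a patient from the repeated-measures model or the Bayesian analysis; both use the remaining visits.

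**Conclusion.** The point holds as a conditional defect in the derivation rule. The algebra is exact and free of assumptions: an intensity in a region with area score 0 cannot affect PASI, and the last step nevertheless discards the score if that item is blank. Whether this costs anything depends on one assumption that the documents cannot settle, namely that such blanks exist after cleaning. If none exist, the effect is nil. If one exists, the cost is a single visit after baseline, or all of one patient's PASI results relative to baseline if it falls at Day -1.

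The importance is minor. PASI is a secondary endpoint, the study tests no formal hypotheses, and no sample size, error rate or power figure is affected. The change is worth making because it recovers known scores in groups of six without imputing anything, and because a rule fixed in advance avoids deciding about blanks once treatment is known.

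**What to change.** Replace the last step of the PASI derivation in SAP 8.3.1 with: *If PASIAREA = 0 for a region, set that region's contribution to 0. Set PASI to missing only if an area score is missing, or an intensity score is missing in a region with area > 0.*

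This costs one line of SAP text and one line of code, with no new data and no imputation. To cover the risk of a wrongly entered 0, list every visit at which a region has area score 0 with blank intensities, and check those area scores during data cleaning. If the listing is empty, the results are identical to those under the present rule.
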